
boosting their confidence in their parenting abilities, and giving them new insights into how to understand and respond positively to their children's communication. This effect was reflected in the quantitative data on changes in parental sensitivity in the intervention and control groups, as shown in Figure 1 in the attachment. Ratings of parental sensitivity were conducted based on analysis of video data by a psychologist who was blind to intervention allocation, with clear positive intervention effects. In the group who received VIPP, just 35% were rated as sensitive in their interactions with their children at baseline; this rose to 50% at the 5-month follow-up (postintervention) and 64% at the 8-month follow-up. By contrast, in the control condition mothers who did not receive VIPP, average levels of sensitivity dropped over time. Whilst 50% of control mothers were rated as sensitive in their interactions with their children at baseline, this dropped to 44.5% at the 5-month follow-up and 33.25% at the 8-month follow-up.

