3 STUDY DESIGN

Case series of N = 10 mothers using perinatal mental health services and offered our adapted version of VIPP. Case series are useful for establishing the feasibility of a novel or adapted intervention (Kooistra et al. 2009, Stewart et al. 2019). They are often used for piloting and gaining feedback on adapted versions of intervention protocols before moving to conducting a full randomised controlled trial. For instance in our previous study we piloted an adapted version of VIPP for parents experiencing personality-related mental health difficulties in 9 mothers, before moving to test it in a trial; and the ACORN study piloted an adapted version of the Towards Parenthood intervention in a small case series of pregnant women before moving to test it in a trial (ISRCTN10052006; Wilkinson et al. 2016). We will follow guidance on designing high quality case series by using a prospective design; clearly defining our population, intervention, outcomes, and follow-up; and not making causal inferences about the treatment effect (Kooistra et al. 2009). Our planned sample size of 10 follows established good practice in carrying out case series in previous related research (ISRCTN10052006; Wilkinson et al. 2016) and in the wider literature, where case series usually have 10 or fewer participants with the average being 8 (Abu-Zidan et al. 2012). Additional mothers will be recruited should initial recruits discontinue the intervention prematurely or be lost to follow-up.

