- 6) Parental sensitivity. This will be rated by a trained researcher based on video data of parent-child interaction, using the Parent-Infant Interaction Observation Screen. This is an observational coding tool that provides a measure of parental sensitivity based on 3 to 4 minutes of video footage. It has demonstrated good internal consistency and inter-rater reliability, and convergent validity with other measures of parent-child interaction (Svanberg et al. 2013).
- 7) Therapeutic alliance. This will be assessed using the Helping Alliance Questionnaire-II (HAQ-II). This is a 17-item self-report scale, with a service-user completed version and a clinician-completed version, assessing the quality of the therapeutic alliance between the service-user and the clinician. The measure has demonstrated good internal consistency and convergent validity with other measures of the alliance (Luborsky et al. 1996).

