7.1 Sample size

The case series size of N = 10 mothers follows established good practice in carrying out case series in previous related research (ISRCTN10052006; Wilkinson et al. 2016) and in the wider literature, where case series usually have 10 or fewer participants with the average being 8 (Abu-Zidan et al. 2012). Additional mothers will be recruited should initial recruits discontinue the intervention prematurely or be lost to follow-up.

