7.3 Analysis plan

Qualitative analysis. The interview transcripts will be analysed using thematic analysis (Braun & Clarke 2006), by a research assistant and by [name], a service-user researcher who has previously co-analysed the qualitative feedback interviews generated during BOOST. Analysis will be supported by NVivo coding software. We will use the findings to make judgements about intervention acceptability and feasibility for mothers and clinicians, any facilitators and barriers to this, and any further minor modifications to the protocol that may be helpful.

Quantitative analysis. We will establish objective indices of feasibility and acceptability by determining:

- 1) % of trained clinicians implementing at least 1 VIPP intervention case
- 2) % of mothers invited to participate who give informed consent to do so
- 3) % of mothers initiating and completing the VIPP intervention
- 4) mother and clinician ratings of the therapeutic alliance during VIPP

We will calculate effect sizes and standard deviations for improvement in maternal sensitivity, parenting stress, parental self-efficacy and the parent-child bond from pre- to post-intervention. We will then combine these parameters with data on older infants (6 months plus) from BOOST in order to calculate the sample size required in a definitive randomised controlled trial. Additionally, we will compare the obtained effect sizes to those obtained when using the standard VIPP protocol in this population during BOOST, to check whether there is any evidence that the changes to the intervention protocol have led to dilution of intervention effects. For instance, in the BOOST trial, the percentage of mothers receiving VIPP who were rated as sensitive increased by 15% from pre-post intervention; by contrast the percentage rated as sensitive in the control group who did not receive VIPP deteriorated by 17%. Thus if the percentage of mothers rated as sensitive does not increase, or deteriorates, from pre-post intervention using the adapted protocol, we will consider this as potential evidence that the adapted intervention effect has been diluted relative to the standard protocol.

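### Section 7.3 reads no rise in the percentage of mothers rated sensitive as a sign of dilution, but in about 10 uncontrolled mothers that threshold discriminates poorly, and the control figure beside it is from a different time point

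*Protocol*

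**What the plan says.** Section 7.3 plans to compare pre-post effect sizes in this case series with those from BOOST, to see whether adapting VIPP has weakened it. As an example it recalls that in BOOST "the percentage of mothers receiving VIPP who were rated as sensitive increased by 15% from pre-post intervention", while the control group fell by 17%. It then sets the reading: "if the percentage of mothers rated as sensitive does not increase, or deteriorates, from pre-post intervention using the adapted protocol", the team will treat the result as a possible sign that the adaptation has weakened VIPP. The sentence carries no interval, margin or error rate.

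The BOOST figures are in section 1. In the VIPP arm "just 35% were rated as sensitive in their interactions with their children at baseline; this rose to 50% at the 5-month follow-up". Controls went from 50% at baseline to 44.5% at 5 months and 33.25% at 8 months. BOOST had 34 women in all.

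On size, section 7.1 says "The case series size of N = 10 mothers follows established good practice in carrying out case series". Sections 3 and 7.1 allow extra mothers to be recruited if some discontinue or are lost, and section 7.4 analyses everyone recruited, so the final number may be slightly above 10. The post-intervention assessment is 5 months after baseline (section 6.5.1). The secondary objective in the study summary already promises pre-post effect sizes with confidence intervals, and it lists the Parent-Infant Interaction Observation Screen among its measures.

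**The concern.** The protocol fixes both a threshold (zero net change) and its interpretation (possible dilution). To be useful, the reading should be rare when the adapted version works as well as the standard one and common when it does not. With about 10 mothers, the whole benchmark effect is a net gain of 1.5 mothers, so one or two changed ratings decide the outcome.

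The choice of zero also depends on what would happen without VIPP. If untreated mothers tend to decline, holding steady may itself be a benefit. The control figure beside the rule therefore matters, and it appears to come from a later visit than the VIPP figure.

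The findings are meant to inform a planned randomised trial. A sound adaptation could be described as diluted, or a weakened one could reassure the team, on the strength of chance.

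**Working it through.** **1. The protocol's benchmarks, from section 1.**

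- VIPP, 5 months: 50 − 35 = +15 points. This matches section 7.3.
- Control, 8 months: 33.25 − 50 = −16.75, about −17 points. This matches section 7.3.
- Control, 5 months: 44.5 − 50 = −5.5 points. This is not quoted in section 7.3.

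Both figures in section 7.3 reproduce, but they belong to different visits. The VIPP change and this study's post-intervention assessment are at 5 months; the control change is at 8 months.

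**2. Model for the flag.** Each mother is rated sensitive or not, before and after. Let g be the probability that she gains the rating and l the probability that she loses it, so the true change is g − l. With n = 10, G gains and L losses, the flag is raised when G ≤ L:

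P(flag) = Σ over a ≤ b of [10! / (a! b! (10−a−b)!)] g^a l^b (1−g−l)^(10−a−b)

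The protocol does not give l. I assumed values from 0 to about 0.2. Independent ratings at 35% and 50% correspond to l = 0.35 × 0.50 = 0.175 and g = 0.65 × 0.50 = 0.325.

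Hand check at l = 0: the flag needs no gains at all, so P = 0.85^10 = 0.197 for +15 points and 0.925^10 = 0.459 for +7.5 points.

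**3. Probability of a flag, n = 10.**

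| True pre-post change | l = 0 | l = 0.05 | l = 0.10 | l = 0.175 | l = 0.20 |
|---|---|---|---|---|---|
| +15 (as BOOST) | 19.7% | 25.3% | 28.8% | 32.1% | 32.9% |
| +7.5 (half the rise) | 45.9% | 43.6% | 44.1% | 45.0% | 45.2% |
| 0 (no change) | 100% | 72.5% | 64.7% | 60.7% | 59.9% |

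The 100% entry is the degenerate case in which no mother ever changes rating. Otherwise no change escapes with probability 27.5% (l = 0.05) to 40.1% (l = 0.20). With independent ratings at 35% both times (g = l = 0.65 × 0.35 = 0.2275) it escapes 40.7% of the time.

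**4. Weight of a flag** (ratio of flag probabilities against +15):

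- No change: 72.5/25.3 = 2.9 at l = 0.05; 64.7/28.8 = 2.2 at 0.10; 60.7/32.1 = 1.9 at 0.175.
- Half the rise: 43.6/25.3 = 1.7; 44.1/28.8 = 1.5; 45.0/32.1 = 1.4.

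**5. Precision.** The approximate 95% half-width for the change is 1.96 × √[(g + l − (g − l)²)/10]. For a true +15 it is 22 points at l = 0 (√[(0.15 − 0.0225)/10] = 0.113), 30 at l = 0.05, 36 at l = 0.10 and 43 at l = 0.175. Every one exceeds the 15-point effect.

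**6. Would a few more mothers help?** At l = 0.10 and n = 12 the three flag probabilities are 25.4%, 41.2% and 63.3%, so modest replacement recruitment changes little. Because the threshold is zero, the flag rate under no change tends to 50% as n grows; size alone does not repair the rule.

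**The case against.** The best defence is that the rule is modest. It is offered as one example within a wider comparison of effect sizes, and its only stated consequence is a hedged one. That stands, and it limits the severity. A reader might infer a go/no-go criterion for the definitive trial, but no section makes that trial conditional on it.

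A reader might also call the flag pure noise. The figures do not support that: no change is flagged about two to three times as often as an undiluted effect. On BOOST's own control data a wholly ineffective version would be expected to fall by 5.5 points rather than hold steady. It would be flagged more often still, about 68% to 83% of the time outside degenerate cases. The weakness is greatest for partial dilution.

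Three further criticisms are tempting and should not be pressed:

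- **Conflict with section 3.** That section commits to "not making causal inferences about the treatment effect". Linking a flat result to the adaptation sits uneasily with this, but wording in terms of potential evidence is a tension, not a contradiction.
- **Masking.** BOOST videos were rated "by a psychologist who was blind to intervention allocation"; here, "This will be rated by a trained researcher based on video data of parent-child interaction". BOOST's masking was between arms, and a single-arm series has no allocation to mask. The protocol does not say that BOOST raters were blind to visit.
- **Ten-point steps.** That exactly +15 cannot be observed in 10 mothers is irrelevant to a threshold of zero.

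Finally, intervals for pre-post change are already promised in the secondary objective. The gap is that the dilution reading does not use them.

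**Conclusion.** The concern holds in this form: the zero-change reading in section 7.3 discriminates poorly, and its control benchmark is from the wrong visit.

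For about 10 mothers, with a probability of losing a sensitive rating between 0 and about 0.2, an undiluted version is flagged about 20% to 33% of the time and a version with half the rise 44% to 46%. A version with no pre-post change escapes about 28% to 41% of the time when discordance is not zero. A flag multiplies the odds of complete loss of effect against no dilution by about 2 to 3, and those of half loss by only 1.4 to 1.7 (l = 0.05 to 0.175). These results assume independent mothers and take the BOOST +15 as exact, although it comes from one arm of a 34-woman trial.

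The −17 should be −5.5 at the matching visit. Since controls declined, zero change need not mean that the benefit is lost, and a study without controls cannot tell.

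Severity is should-fix. The comparison is secondary and hedged, and the primary feasibility and acceptability outcomes do not depend on it.

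**What to change.** In section 7.3:

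1. Remove the zero-change reading, or label it descriptive only.
2. Report the paired change in the Parent-Infant Interaction Observation Screen, and the percentage rated sensitive, with the confidence intervals already promised in the secondary objective. Set them beside the BOOST VIPP-arm 5-month change with its own interval.
3. Replace the control decline of 17 points with the 5-month change of −5.5 points.
4. State that about 10 mothers can neither confirm nor exclude dilution.

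Rating the videos in random order with the visit label removed is optional good practice. It does not follow from BOOST's allocation masking, and it would be partial because infants visibly age.

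The cost is wording, plus intervals for BOOST data that the plan already intends to use; no new participants are needed. The sponsor gives up a simple signal of dilution.

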7.4 Subject population

Data from any participant recruited into the study will be analysed, regardless of whether they received any sessions of the allocated treatment (intention-to-treat analysis).

8 **MONITORING, AUDIT & INSPECTION**

The study will be subject to monitoring, auditing and inspection by the sponsor or the sponsor's delegated representatives and the relevant authorities responsible for each of the sites where the research will take place. The purpose of the monitoring is to ensure that the study is conducted in accordance with the authorised study protocol, the principles of GCP and all applicable regulations.

The sponsor and regulators will require access to the study site for these inspections which will be supervised by the site investigator(s). The inspection activities apply to the following, and associated. areas in order to:

- review the study master/site file (hard and soft copies);
- review the study participant consent forms;
- review research documents as approved by applicable regulatory body and those referenced in protocol;
- review participant facing, current and superseded versions;
- review study measures and assessments as completed by participants;
- view the storage facilities/spaces for research documentation (paper and electronic);
- review site delegation of duties log;
- review trial amendment log.

9 ETHICAL AND REGULATORY CONSIDERATIONS

9.1 Research Ethics Committee (REC) review& reports

Before the start of the trial, approval will be sought from a REC and from the relevant NHS R&D departments for the trial protocol, informed consent forms and other relevant documents e.g. advertisements and GP information letters

Substantial amendments that require review by REC will not be implemented until the REC and the relevant NHS R&D departments grant a favourable opinion for the study.

All correspondence with the REC will be retained in the Trial Master File/Investigator Site File

An annual progress report (APR) will be produced by the Chief Investigator and will be submitted to the REC within 30 days of the anniversary date on which the favourable opinion was given, and annually until the trial is declared ended. The Chief Investigator will notify the REC of the end of the study. If the study is ended prematurely, the Chief Investigator will notify the REC, including the reasons for the premature termination. Within one year after the end of the study, the Chief Investigator will submit a final report with the results, including any publications/abstracts, to the REC

9.2 **Public and Patient Involvement**

Patients and members of the public have been, and will be, involved in the Design, Management, Undertaking and Analysis of the research.

The PPI lead for the project will be [name]. [name] will draw on her lived experience of using mental health services in addition to her previous experience analysing the feedback given by mothers who took part in BOOST, to share insights with the clinicians being BOOST-2 Boosting Baby Communication & Play Protocol V1.1 Date 22-06-2021

BOOST-2 Boosting Baby Communication & Play

trained on how mothers experience the intervention and how mothers' anxieties around video feedback can best be addressed. During the study, [name] will draw on her experience of using qualitative interviewing and analysis to lead on interviewing participating mothers, to understand how they experienced the intervention and any challenges faced.

Additionally, we have recruited 3 mothers who have experience of using perinatal mental health services — 1 of whom received the VIPP intervention during the previous BOOST study - who will form the PPI panel for the study. We have shared the plans for the study with them and they have provided feedback as well as reviewing the draft participant information sheets. We have incorporated their feedback to improve our ability to engage mothers and ensure they are well-informed and reassured about what the study involves. For instance, the Mum who had received VIPP emphasised how anxious potential participants may be feeling about who will see the videos and whether they will be judged. Following this feedback, we have added additional information about who will see the videos, data protection and confidentiality, and have added quotes from mothers who took part in BOOST explaining how positive and non-judgemental they found the intervention.

The panel will meet again in the middle of the study to help us analyse early feedback data from participating mothers, and once at the end to help us interpret the study findings and decide how to take them forward.

9.3 Data protection and patient confidentiality

All investigators and trial site staff will comply with the requirements of the Data Protection Act 1998 and the General Data Protection Act (2018) with regards to the collection, storage, processing and disclosure of personal information and will uphold the Act's core principles.

All electronic data files will be pseudonymised (i.e. identified only by a participant code and containing no other identifiable data). These will be stored only on City University of London's Egress system and accessible only to the research team. The pseudonymised information and identification key will be stored separately so that participants cannot be easily identified.

Any paper-based data will be stored in a locked filing cabinet at City University of London.

Video data will be stored securely in a private and secure encrypted zone on City University of London's Egress system and will only be accessible by the research and clinical team involved in this project. Please see here for more information about Egress: https://www.egress.com/secure-file-sharing/collaboration

All personal data will be kept only for 12 months after the end of the study in order to allow dissemination of a summary of study findings to participants. Additionally, participants will be able to opt-in to allow their contact details to be stored for 10 years after the research so that the researchers can let them know if they are doing any more research related to parents and children that may be of interest to them. All pseudonymised and video research data will be stored for 10 years and then destroyed, in accordance with the International Committee of Medical Journal Editors' recommendation (ICMJE 2016) that primary research data should be retained for a minimum of ten years so that it can be used to address any questions from patients, clinicians, academics or the public that arise from the publication of the study findings.

9.4 Indemnity

The study will provide indemnity through the City University of London insurance scheme should liability arise as a result of the study management, design or conduct.

9.5 Amendments

The Chief Investigator [name] will be responsible for the decision to amend the protocol and will liaise with the sponsor to decide whether an amendment is substantial or non-substantial.

The Health Research Authority will be notified of all amendments. Only those amendments labelled as substantial will be sent to the REC for review and favourable opinion.

Substantial amendments will be made using the Notice of Substantial Amendment form within IRAS and Non-substantial amendments will be made by completing an NHS REC Notification of Amendment form.

All amendments will detail the rationale for and nature of the amendment, and will be supported by the revised versions of the protocol and participant documents, as apllicable, with new version numbers and dates.

Both the Notice of Substantial Amendment form and NHS REC Notification of Amendment form and the amended protocol and participant documents will be sent to the sponsor for approval and then submitted to the Health Research Authority, if applicable, to the NHS REC who provided the original approval for the study, and to the R&D departments of the participating NHS Trusts.

Amendments will not be implemented until approval has been obtained from all of these bodies.

All amendments will be recorded on an amendment log within the trial master file and all investigator site files which outlines with the amendment number and date and reason of the amendment and documents that have been modified for the amendment

9.6 Post study care

The NHS Trusts from which participants were recruited will be responsible for provision of care as appropriate, including access to mental health services and psychological treatments, once the study is complete.

Participating clinicians will determine whether to continue to offer the study intervention (video feedback for positive parenting) to patients once the study is complete – however, there are no special funding arrangements in place to enable this, and we do not yet know whether the intervention is feasible to deliver or effective.

